### 3.3 Summary of Activities and Assessments

**Table 2 – Schedule of Activities and Assessments, Modified from CSP 2017-1 Table 4**

Evaluation	Initial Screen	Rescreen 	Day 1 (baseline) 	1-h post-infusion ±15 min	6-h post-infusion -1 or +2 h	Day 2 24-h post-infusion ±3 h	If hospitalized			Day 6 (+4 d)	Day 30 (+2 d) (via phone)
							Day 3	Day 4	Day 5		
Visit Number:	1	1A	2	3	4	5	6	7	8	9	10
Sign informed consent form	X										
Verbally reconfirm consent		X	X	X	X	X	X	X	X	X	X
Medical history and complete physical exam 	X										
WHO bleeding severity	X	X	X	X	X	X				X	
Abbreviated physical exam 		X	X	X	X	X				X	
Pregnancy test (female only)	X	X									
Concomitant medications 	X	X	X	X	X	X	X	X	X	X	
Record transfused blood products 	X	X	X	X	X	X	X	X	X	X	
Thrombosomes infusion			X								
Vital signs 	X	X	X	Prior to infusion, then every 15 ±5 min after start of infusion until 2 h. Continue every 1 h ±5 min until 4 h, then at 6 h and 24 h ±10 min post-infusion.						X	
Pulse oximetry			X	Monitor continuously during vital signs assessment; record at same time-points as vital signs.							
Monitor for AEs			X	Prior to infusion, then every 15 ±5 min after start of infusion until 2 h. Continue every 1 h ±5 min until 4 h, then at 6 h and 24 h ±10 min post-infusion. Continue daily monitoring until discharged or Day 6.				X	X	X	X 
12-lead EKG 	X		X 		X						
Hematology CBC 	X	X	X	X	X	X	Daily CBC, at minimum		X		
ABO group, Rh type	X										
Coagulation testing 	X	X	X	X	X	X					
Routine chemistry 			X		X	X					
Special chemistry 			X		X	X					
Draw archive sample 	X									X	

Abbreviations: ABO, blood types A, B, and O; AE, adverse event; ALT, alanine transaminase; aPTT, activated partial thromboplastin time; AST, aspartate transaminase; BUN, blood urea nitrogen; CBC, complete blood count; EKG, electrocardiogram; GGT, gamma glutamyl transferase; hs, high sensitivity; INR, international normalized ratio; LDH, lactate dehydrogenase; MPV, mean platelet volume; PF, prothrombin fragment; PT, prothrombin time; RBC, red blood cell; Rh, Rhesus; ROTEM, rotational thromboelastometry; SAE, serious adverse event; TAT, thrombin antithrombin; TEG, thromboelastography; TGA, thrombin generation assay; WBC, white blood cell; WHO, World Health Organization.

-  Complete rescreening will be performed on patients who preliminarily met eligibility criteria but were not actively bleeding at the time of initial screening and then started bleeding within 4 weeks. Patients who continue/begin bleeding and fully meet eligibility criteria within 4 days (+6 hours) of initial screening will not need require rescreening, except for re-assessment of WHO bleeding and CBC.
-  Baseline may occur within 24 hours following initial screening (or rescreening). The WHO bleeding severity, CBC, and coagulation assessments are required at baseline, not more than 2 hours prior to infusion. Red cell transfusion must be specifically related to treatment of bleeding within 24 hours of onset of bleeding.
-  Chart review for SAEs will occur from Day 1 through Day 30 (+2 days). Phone calls with the patient will occur to confirm whether the patient experienced an SAE or required emergency medical care at an outside facility.
-  Complete physical examinations will include measuring height and weight, documenting medical history, and performing a general medical/neurological examination. Medical history will include previous transfusions with red blood cells, plasma, and/or platelets.
-  Abbreviated physical examinations will include general appearance, cardiovascular, respiratory, extremity, abdomen, and head and neck assessments.
-  Blood products may include packed red blood cells, whole blood, apheresis platelets, pooled whole blood derived platelets, cryoprecipitate, and plasma. In the event of a blood product transfusion occurring after Thrombosomes infusion on Days 1-6, CBC results will be required from a blood sample collected within 8 hours prior to transfusion and within 1 hour (+30 min) following transfusion.
-  Hematology CBC analytes will include WBC, RBC, hemoglobin, hematocrit, platelets, MPV, neutrophils, lymphocytes, monocytes, eosinophils, and basophils. Daily CBC will be required, but all CBC data for each patient during hospitalization through Day 6 will be collected.
-  During screening, coagulation testing will include only PT/INR, aPTT, D-dimer, and fibrinogen. At and following baseline, testing will include PT/INR, aPTT, D-dimer, fibrinogen, TAT, PF 1+2, TEG or ROTEM, and TGA. For baseline testing, PT/INR, aPTT, D-dimer and fibrinogen will be collected no more than 8 hours prior to infusion.
-  EKG measures include only heart rate and QT interval with Fridericia's correction. The EKG will be repeated if performed more than 4 days before infusion.
-  For each of the time-points that require archive samples, 2 10-mL samples will be drawn (1 for plasma and 1 for serum).
-  Medications may include but will not be limited to over-the-counter remedies, herbal preparations, vitamins, supplements and intravenous fluids.
-  Vital signs will include heart rate, respiratory rate, systolic and diastolic blood pressure, and body temperature.
-  Routine chemistry will include Na, K, Cl, CO2, glucose, BUN, creatinine, albumin, total bilirubin, Ca, AST, alkaline phosphatase, ALT, GGT, LDH, total cholesterol, and total protein. Special chemistry will include hs Troponin I and hs Troponin T.

## **4 SAMPLE SIZE CONSIDERATIONS**

The sample size for this Phase 1 study was not statistically derived. Rather, the target sample size of 8 evaluable patients per each of 3 escalating infusion dose levels was selected to minimize the number of patients exposed to the study treatment and associated assessments, while also ensuring access to a reasonable number of study subjects to support the study's primary and secondary objectives. Importantly, patients will be considered "evaluable" based on satisfaction of the criterion for inclusion in the most restrictive analysis population, requiring completion of the target post-infusion follow-up of 6 days (see Section 5.3, Evaluable Population). Target sample sizes for individual study sites contributing to each patient cohort will adhere to a ratio-based rule-of-thumb of 1:5, which defines an upper threshold for the relative difference (or degree of imbalance) between the smallest (or lowest enrolling) and largest (or highest enrolling) sites (Ruvuna 2004). In applying this rule, enrollment at the largest site(s) may not exceed 5 times the enrollment at the smallest site(s) within each of the 3 Thrombosomes dose levels.

## **5 ANALYSIS POPULATIONS**

### **5.1 Screened Population**

The Screened Population will include all patients who provide written informed consent for study participation. Patients who withdraw consent, who do not complete all screening (or rescreening) assessments, who are ultimately verified as ineligible (based on unsatisfied inclusion criteria or satisfied exclusion criteria), and/or who do not receive the Thrombosomes infusion (e.g., when awaiting the infusion in queue for 4 weeks past the start of screening) will be classified as screening failures. The Screened Population will be used in descriptive analysis of the numbers of patients screened and failing to enter the study, both overall and by primary reason for failure.

### **5.2 Safety Population**

The Safety Population will include all patients who were infused with Thrombosomes, regardless of duration of subsequent study participation or adherence to planned follow-up assessments. As patients will be considered enrolled at the start of infusion, the Safety Population will also represent an "enrolled population". The population will be used in descriptive analysis of patient characteristics and disposition, as well as in all safety analyses supporting the Primary Objective and select efficacy analyses supporting the Secondary Objective.

### **5.3 Evaluable Population**

The Evaluable Population will include all patients from the Safety Population who completed the planned Day-6 follow-up visit (on Day 6 +4 days) and, thus, were classified as "evaluable". The Evaluable Population will be used, along with the Safety Population, in select efficacy analyses supporting the Secondary Objective.

## **6 CONSIDERATIONS FOR DATA HANDLING AND ANALYSIS**

### **6.1 Programming Environment**

All data manipulation and statistical analyses will be performed using SAS statistical software (version 9.4 or later; SAS Institute Inc., Cary, NC).

## 6.2 Nominal Visits and Visit Windows

For each patient, infusion of Thrombosomes will occur on Day 1. Screening, baseline (pre-infusion), and post-infusion activities and assessments will correspond to specific nominal visits and time-points, as shown below in **Table 3**. Note that each nominal visit/time-point has an associated window, defined as the range in time (e.g., study days, hours, or minutes) during which the scheduled activities or assessments must be performed. Activities and assessments performed outside of these windows will be labeled “unscheduled”. Data collected from unscheduled activities/assessments will be incorporated into patient-level data listings but will not necessarily be included in population-level data summaries (i.e., tables and/or figures) presented by visit/time-point. As appropriate (e.g., depending on sample size), data from unscheduled visits/time-points will be either entirely excluded from data summaries or compiled between scheduled visits/time-points for intermixed scheduled/unscheduled data presentation.

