Routine Chemistry: Na, K, Cl, CO2, Glucose, BUN, Creatinine, Albumin, Total Bili, Ca, AST, Alkaline Phosphatase, ALT, GGT, LDH, Total Cholesterol, Total Protein			X		X	X					
Special Chemistry hsTroponin I or T Assay			X		X	X					
Draw archive sample	X									X	

Evaluation	Initial Screen	Rescreen (if applicable  )	Day 1  Base Line -2 hr pre-infusion	1 hr post infusion ± 15min	6 hr post -1 or +2 hr	Day 2 24 hr post ± 3 hr	If hospitalized			Day 6 (+ 4 days)	Day 30 (+2 days) (by phone)								
							Day 3	Day 4	Day 5										
 Rescreening performed on those patients who passed eligibility criteria, were not actively bleeding at time of initial screen, and started bleeding within 4 weeks. Patients who were initially screened within 4 days (+6 hrs) do not need to be re-screened except for WHO bleeding assessment and CBC.																			
 Baseline may occur on the same day (within 24 hours) as either Initial Screen or Rescreen. The WHO assessment, CBC and coagulation must be collected at baseline, not more than 2 hours prior to infusion. Red cell transfusion must be specifically related to treatment of bleeding within 24 hours of onset of bleeding.																			
 Chart review for SAEs (only) needs to include data from day 1 though Day 30 (+2 days). Phone call with patient is to confirm if the patient had an SAE or required emergency medical care at an outside facility.																			
 Complete physical exam to include height, weight, general assessment of health by history and medical exam including neurological exam. History to include previous transfusion with red blood cells, plasma and/or platelets.																			
 Abbreviated Physical Exam to include general appearance, cardiovascular, respiratory, extremities, abdomen and head and neck.																			
 In the event of the transfusion of a blood component after infusion of Thrombosomes on Days 1-6, CBC results are required from a sample collected within 8 hours or less prior to the transfusion and within 1-hour (+30 min) post transfusion.																			
 Daily CBC required, but ALL CBC data for each patient during the hospitalization phase through Day 6 must be collected and entered into the database.																			
 If TEG or ROTEM testing is available, include samples for the record.																			

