#### **1.15.6.2 *Blood Sampling/Testing***

- A. Additional tests for evaluation and/or treatment of safety and/or laboratory events may occur. The additional tests will be determined by the patient's signs, symptoms or review of laboratory data, and will not be dictated by the protocol. A recommendation for the need for additional testing will be made by the patient's treating physician. The patient must agree to the additional tests before these tests can be performed.
- B. Label all blood tubes following sites standard operating procedures (SOP) and patient study ID number, date, time and visit number.
- C. Send samples for testing following site's SOP.

D. Complete Adverse Event Form that includes description of the event, relatedness, start date, stop date, medications used to treat and results of laboratory testing.

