## 2.2 Study Endpoints

### 2.2.1 Primary Endpoints

Several primary endpoints will be quantified per patient cohort (i.e., by dose level), as well as overall (i.e., across all 3 dose levels):

- Overall frequency of (and number and percentage of patients who experience) TEAEs and TESAEs, including serious adverse drug reactions and treatment-related events specifically defining the study's suspension and stopping rules (i.e., thromboembolic events, acute lung injury, anaphylaxis, and death).
- Numbers and percentages of patients by highest WHO bleeding severity grade at baseline and post-baseline time-points, by highest severity grade at post-baseline time-points relative to baseline (allowing for assessment of shift), by both highest severity grade and bleeding site at baseline and post-baseline time-points, and by indication of a maximum severity grade  $\geq 2$  across bleeding sites at post-baseline time-points.
- Numbers and percentages of patients by grade-level change in WHO bleeding severity (e.g., -2, -1, 0, +1, +2, +3) from baseline to post-baseline time-points for the patient's most severe bleeding site at baseline, by indication of increased bleeding severity from baseline to post-baseline time-points for the patient's most severe bleeding site at baseline, and by indication of newly-developed bleeding sites from baseline to post-baseline time-points.
- Statistics describing (and/or graphics showing) central tendency and variability in coagulation, hematology, and serum chemistry measures across patients at baseline and post-baseline time-points, allowing for assessment of directional change in measures over time.
- Number and percentage of patients who shift from normal or clinically non-significant abnormal findings to clinically significant abnormal findings in coagulation, hematology, or serum chemistry measures between baseline and post-baseline time-points.
- Statistics describing central tendency and variability in vital signs, oxygen saturation (per pulse oximetry), and select 12-lead electrocardiogram (EKG) measures across patients at baseline and post-baseline time-points.
- Number and percentage of patients who shift in category of overall EKG interpretation from normal or clinically non-significant abnormal to clinically significant abnormal between baseline to post-baseline time-points.

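### Laboratory and EKG results outside the visit windows can be left out of every shift count, so the number of patients with a clinically significant shift may be understated

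*SAP*

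**What the plan says.** SAP 6.2 gives each nominal time-point a window (Table 3). Anything done outside its window is labelled unscheduled. Such data go into the patient listings but "will not necessarily be included in population-level data summaries" by visit. The section then leaves the handling to judgement, with sample size as its example criterion: "data from unscheduled visits/time-points will be either entirely excluded from data summaries or compiled between scheduled visits/time-points". It gives no threshold, no time for the decision and no one to make it.

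SAP 2.2.1 lists among the primary endpoints: "Number and percentage of patients who shift from normal or clinically non-significant abnormal findings to clinically significant abnormal findings". This item covers coagulation, hematology and chemistry, and a parallel item covers the overall EKG interpretation. SAP 8.3 lays out the laboratory shifts by measure and visit, and SAP 8.4 lays out the EKG shifts by time-point. Neither section, nor any table title in SAP Appendix 2, provides a row for the worst or any post-baseline result.

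Results between windows are foreseeable. Protocol 1.15.6.2 says: "Additional tests for evaluation and/or treatment of safety and/or laboratory events may occur", prompted by signs, symptoms or laboratory review. Protocol Table 4 requires CBCs around any transfusion on Days 1-6, and its footnote 7 adds that "ALL CBC data for each patient during the hospitalization phase through Day 6 must be collected and entered into the database". SAP 8.7 sends unscheduled and out-of-window assessments to a listing.

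**The concern.** The shift endpoint asks how many patients moved to a clinically significant abnormal result after infusion. A test ordered because something looks wrong is more likely than a routine one to show such a result. If it falls between windows and the exclusion option is taken, the patient can have a real shift that no row counts. For a count of patients with a shift at any time, leaving results out can lower the number but cannot raise it.

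A plain timing slip has a related effect. The only scheduled post-infusion EKG is at 6 hours, with a window of 5 to 8 hours. If it is recorded at 8.5 hours and excluded, that patient has no post-infusion EKG in the shift table at all.

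The SAP is also uneven on this point. For the efficacy hematology categories, SAP 9.1 considers every measurement in the timeframe. The safety shifts have no equivalent rule.

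**Working it through.** The plan states no figure to reproduce: SAP section 4 says that the sample size was not statistically derived. The check is of coverage first, then of size.

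**1. How much of the early period the windows cover.** From SAP Table 3:
- 1 h ± 15 min: 0.75 to 1.25 h = 0.5 h
- 6 h, -1 to +2 h: 5 to 8 h = 3 h
- 24 h ± 3 h: 21 to 27 h = 6 h

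With the schedule of events (Protocol Table 4, SAP Table 2):

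| Test | Scheduled post-infusion windows | Hours covered | Share of first 27 h | Share of first 48 h |
|---|---|---|---|---|
| Coagulation | 1, 6, 24 h | 0.5 + 3 + 6 = 9.5 | 9.5/27 = 35.2% | 9.5/48 = 19.8% |
| Chemistry, troponin | 6, 24 h | 3 + 6 = 9 | 9/27 = 33.3% | 9/48 = 18.75% |
| EKG | 6 h | 3 | 3/27 = 11.1% | 3/48 = 6.25% |

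The first 27 h ends with the last of these windows; 48 h is the stopping-rule period. These are shares of clock time, not of results.

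**2. Where example results would go.**
- Troponin at 12 h: outside 5-8 h and 21-27 h, so unscheduled.
- EKG at 3 h: outside 5-8 h, so unscheduled.
- 1-hour coagulation sample drawn at 80 min: outside 45-75 min, so unscheduled.
- CBC in hospital on Day 4: the window is the whole day, so in window.
- CBC on Day 8: inside the Day 6 window (Days 6-10), so in window.

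The gap therefore lies mainly in Days 1-2, plus coagulation, chemistry/troponin and EKG afterwards, because none of these has a scheduled test after Day 2.

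**3. Effect of one missed patient on an any-time count** (exact Clopper-Pearson 95% intervals):
- Cohort of 8: 1/8 = 12.5% (0.3% to 52.7%) becomes 0/8 = 0% (0% to 36.9%).
- All 24: 1/24 = 4.2% (0.1% to 21.1%) becomes 0/24 = 0% (0% to 14.2%).

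**4. Chance that at least one patient is affected.** The documents give no rate, so p is assumed: the proportion of patients whose only clinically significant shift is at an unscheduled time. The chance of at least one is 1 - (1 - p)^n.

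| Assumed p | n = 8 | n = 24 |
|---|---|---|
| 2% | 14.9% | 38.4% |
| 5% | 33.7% | 70.8% |
| 10% | 57.0% | 92.0% |
| 20% | 83.2% | 99.5% |

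The range is wide because p is unknown. It shows only that, in a trial of this size, the problem need not be common to affect a table.

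**The case against.** The case on the other side is substantial, and much of it limits the point.

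- **Not every symptom-driven test is affected.** A reader might infer that all such tests become unscheduled. Table 3 does not support that: the in-hospital windows on Days 3-5 and the Day 6 window (Days 6-10) are open, and a symptom-driven test can also fall inside the 6- or 24-hour window.
- **Exclusion is an option, not a certainty, and nothing shows that it would be driven by results.** The alternative in 6.2 is to display the data between visits. A reader might infer that the choice is made after the data are seen. The SAP gives no decision time, and its example criterion is the amount of data, not the values.
- **The abnormalities have another tabulated route.** Protocol 1.15.6 requires AEs found at unscheduled evaluations to be documented. Protocol 1.22.6.1 makes laboratory findings that need intervention AEs. SAP 8.1 tabulates AEs without reference to the assessment windows, including those indicated by abnormal coagulation. The DMC receives AE tables and listings of selected laboratory data. A reader might infer that safety signals or stopping decisions could be lost; the documents do not support that, because suspension and stopping rest on SAEs.
- **The shift counts are one item among several.** AEs head the primary endpoints in SAP 2.2.1, and Protocol 1.16 calls the laboratory summaries exploratory.
- **The 12.5 points belong to an any-time count that the SAP does not tabulate.** A 12-hour value would not alter the 6-hour or 24-hour row. Keeping by-visit rows to comparable times is sound practice.

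All of this stands. None of it supplies the missing count. An AE table records what was judged an event, and a listing is not a count. Showing unscheduled data between visits would still not count each patient once.

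**Conclusion.** The point holds as a limited one. SAP 6.2 leaves the handling of out-of-window results to an unspecified discretion, and the shift tables have no row to catch those results. The number of patients with a clinically significant laboratory or EKG shift may therefore be understated, chiefly from results on Days 1-2 and from coagulation, chemistry/troponin and EKG. EKG is the most exposed, with a single scheduled post-infusion recording.

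In an any-time count, the size is 12.5 percentage points of a cohort, or 4.2 of all 24 patients, for each patient missed. How many would be missed cannot be derived from the documents; the probabilities above rest on assumed rates and on patients being independent.

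The defect is confined to the summaries by visit or time-point and the shift counts drawn from them. AE counts, the listings and the stopping rules do not depend on it. It is worth correcting because the correction is cheap and the endpoint is listed as primary.

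**What to change.** Before database lock:

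1. Keep the by-visit and by-time-point rows on in-window data, so that their timing stays comparable.
2. Add to each laboratory and EKG shift table one row giving each patient's worst post-baseline interpretation, using all results, scheduled and unscheduled.
3. In SAP 6.2, replace the choice that depends on sample size with this fixed rule: unscheduled results stay out of the by-visit rows and enter the worst post-baseline row, as well as the listings.

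The cost is one row per shift table (per measure, for the laboratory tables) and a short SAP amendment. No new data, visits or patients are needed.

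The downside is that a worst-value row depends on how often a patient is tested, so patients with more tests have more chances to show a shift. Footnote the row to say so and read it beside the by-visit rows. Samples that are slightly early or late should not be moved to the nearest visit: without a definition of slightly, that would replace one discretion with another.

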**Table 3 – List of Nominal Visits and Time-Points**

Nominal Visit/Time-Point	Scheduled Study Day	Day/Time Window
Screening 	Days -28 to Day -1	Any time during Days -28 to Day -1
Baseline	Day 1	Any time pre-infusion during Day 1 
Thrombosomes Infusion	Day 1	None; represents time-point 0 and provides reference for nominal visits and time-points
1-hour post-infusion	Day 1	±15 minutes
6-hour post-infusion	Day 1	-1 to +2 hours
24-hour post-infusion	Day 2	±3 hours
Day 3 	Day 3	Any time during Day 3
Day 4 	Day 4	Any time during Day 4
Day 5 	Day 5	Any time during Day 5
Day 6	Day 6	+4 days (any time during Days 6-10)
Day 30	Day 30	+2 days (any time during Days 30-32)

 If the patient is not actively bleeding at the time of screening but bleeding occurs within 4 days (+6 hours) of initial screening, the patient will not be rescreened (just WHO bleeding severity and CBC assessments will be repeated). If the patient is not actively bleeding at the time of screening but bleeding occurs >4 days and within 4 weeks of initial screening, the patient will be wholly rescreened and, following verification of eligibility, then enrolled and infused.

 Baseline assessments may occur any time preceding infusion on Day 1, except for the assessments of WHO bleeding severity, CBC, and coagulation. These assessments will be required to occur within the 2 hours preceding infusion.

 Relevant only if the patient is hospitalized.

